#### 1.4 Clinical Data to Date

Plasma concentrations of ruxolitinib cream were determined following topical application of ruxolitinib cream in plaque psoriasis, AA, AD, and vitiligo, mostly using sparse sampling. The exposures of ruxolitinib were generally strength-dependent with moderate intersubject variability.

In Study INCB 18424-201 in plaque psoriasis, the observed systemic bioavailability of ruxolitinib was independent of formulation strength.

In Study INCB 18424-202 in plaque psoriasis, an intensive sampling scheme was used on the last day of treatment to better characterize the PK following topical application. The systemic PK following topical application was characterized by apparent first-order release, modest peak-to-trough excursion (ratio ~2), estimated relative bioavailability of 3% to 5%, and an  $t_{1/2}$  of approximately 3 days. Systemic bioavailability of ruxolitinib cream was shown to be independent of the strength of the cream formulation and %BSA. The PD results from skin biopsies, including markers for Th1, Th17 pathway activation, reduced levels of inducible nitric oxide synthase, and KRT16 transcript levels, suggest that ruxolitinib cream was pharmacologically active at a local but

not systemic level when administered to participants with active psoriasis for 28 days as either a QD or BID regimen and suggest that key pathologic pathways in the psoriatic lesion are favorably impacted by treatment with ruxolitinib cream.

In Study INCB 18424-204 in AA, ruxolitinib trough concentrations increased as percentage scalp involvement increased.

In Study INCB 18424-206 in AD, trough plasma concentrations increased as the strength of ruxolitinib cream and frequency of applications increased. Participants whose plasma concentrations exceeded 125 nM (equivalent to half of the IC50 value based on the effect of ruxolitinib on IL-6) tended to have more extensive skin involvement and highly inflamed AD lesions. However, no correlation was observed between higher ruxolitinib blood levels in these participants and their response to treatment.

In Study INCB 18424-102 in AD patients, steady-state plasma concentrations (based on geometric mean) following BID administration of 1.5% ruxolitinib cream in adolescent participants were similar to that in adult participants.

In Study INCB 18424-211 in vitiligo, plasma concentrations of ruxolitinib increased as the strength and frequency of application of the cream were increased.

The plasma metabolite profile following topical application is generally similar to that observed following oral administration.

### Psoriasis

Study INCB 18424-201: a double-blind, vehicle-controlled, increasing strength, safety, tolerability, PK, and preliminary efficacy study of ruxolitinib cream 0.5% QD (n = 6), 1.0% QD (n = 6), and 1.5% BID (n = 6) in Part 1. Efficacy (change from baseline to Day 28 in mean total lesion scores) was consistently shown for the 1.0% QD and 1.5% BID cohorts compared with vehicle. In Part 2, 1.5% BID showed a change in mean total scores for target lesions compared with Dovonex® (calcipotriene) 0.005% (n = 6) and with Diprolene® AF (betamethasone dipropionate) 0.05% (n = 5) at Day 28.

Study INCB 18424-202: an open-label, multicenter, sequential-cohort, increasing strength, safety, tolerability, PK, PD, and preliminary efficacy study of different regimens of ruxolitinib cream applied for 4 weeks (28 days) to participants based on their BSA: 2% to 7% (1.5% BID; n = 5), 8% to 13% (1.5% BID; n = 5), 14% to 20% (1.5% BID; n = 5), 14% to 20% (1.0% BID; n = 5), and 14% to 20% (1.5% QD; n = 5). The results of this study indicated that all 5 of these regimens were effective in decreasing the individual signs of lesion severity, lesion area, and the overall disease severity of psoriatic plaques.

Study INCB 18424-203: a double-blind, randomized, multicenter, parallel-group, vehicle-controlled dose-ranging study to compare the safety and efficacy of ruxolitinib cream 0.5% (n = 51), 1.0% (n = 49), or 1.5% (n = 49) QD with a vehicle cream (n = 50) when applied for 12 weeks (84 days). Overall, 199 participants were enrolled of which 161 (80.9%) completed the Day 84 visit. Within each active treatment group, the mean scores for the individual and total psoriasis lesion assessments, the PASI, and the PGA, as well as the mean treatable percent BSA decreased from baseline to each subsequent assessment, which indicated an overall lessening of disease severity.

### Alopecia Areata

Study INCB 18424-204: a 2-part study with ruxolitinib cream 1.5% BID applied for 24 weeks. Part A (n = 12) was open-label and Part B (n = 78) was double-blind, randomized, and vehicle-controlled. Participants enrolled in Part B were to receive ruxolitinib 1.5% cream BID or placebo for 24 weeks. If eligible, participants in Parts A and B could have continued on to an open-label extension period (24 weeks) and long-term extension period (48 weeks). The primary endpoint was not met since no significant difference in SALT50 response in terminal hair was observed between the ruxolitinib cream and vehicle groups at Week 24.

### Atopic Dermatitis

Study INCB 18424-206: a double-blind active- and vehicle-controlled study. In total, 306 participants received study treatment in 1 of 6 treatment groups: ruxolitinib cream 0.15% QD (n = 51), 0.5% QD (n = 51), 1.5% QD (n = 51), and 1.5% BID (n = 50), an active comparator group (triamcinolone 0.1% cream BID; n = 51), and a vehicle control group (BID; n = 52). Participants received study drug (ruxolitinib cream or vehicle) for 8 weeks and triamcinolone cream for the first 4 weeks followed by vehicle only for 4 weeks. All participants were offered the option to continue treatment for an additional 4 weeks with ruxolitinib 1.5% cream BID. For the study's primary endpoint (mean percentage change from baseline in EASI score with ruxolitinib 1.5% cream BID at Week 4), ruxolitinib cream 1.5% BID demonstrated a statistically significantly larger mean percentage change (-71.57%) when compared with the vehicle treatment group (-11.90%; p < 0.0001). Also, ruxolitinib 1.5% cream QD and 0.5% QD treatment groups showed statistically significant larger mean percentage changes from baseline in EASI score at Week 4 (-66.72% and -52.80%, respectively) compared with the vehicle treatment group (-11.90%; p < 0.0001). At Week 8, all 4 ruxolitinib treatment groups (-50.24% to -79.01%) had larger percentage improvements (decreases) from baseline in EASI score than the vehicle treatment group (-21.86%). Ruxolitinib cream 1.5% BID (-71.57%) was noninferior to the triamcinolone treatment group (-59.54%) based on the mean percentage change from baseline in EASI score at Week 4, with a numerical trend toward superiority. At Weeks 4 and 8, all ruxolitinib treatment groups had higher percentages of IGA responders than the vehicle treatment group.

In INCB 18424-303, the most frequently reported TEAEs were upper respiratory tract infection in 3 participants (1.6%) and dermatitis atopic, ear infection, gastroenteritis, headache, papule, pruritus, and respiratory tract congestion in 2 participants each (1.0% each). In INCB 18424-304, the most frequently reported TEAEs were application site pain in 5 participants (1.5%), headache and nasopharyngitis in 4 participants each (1.2% each), and application site pruritus, oropharyngeal pain, and upper respiratory tract infection in 3 participants each (0.9% each).

No fatal TEAEs were reported, and few serious TEAEs occurred across the program.

## **1.5 Dose Rationale**

### Topical Dosing:

In addition to the safety pharmacology and toxicology studies that were completed to support development of ruxolitinib cream. The relative bioavailability of ruxolitinib cream was markedly (~ 90%) lower than that following oral administration. In vitro metabolism studies strongly suggest that cytochrome P450 (CYP) 3A4 is the predominant CYP isozyme responsible for the metabolism of Ruxolitinib cream. 1.5% ruxolitinib cream BID was generally found to be the most efficacious regimen in studies with AD and psoriasis (see below) and hence this regimen is also proposed for this trial.

Ruxolitinib cream has been evaluated in over 200 subjects with plaque psoriasis in 3 clinical studies with dosing of 1 to 3 months' duration. Study INCB 18424-201 was a double-blind, vehicle-controlled, rising-dose, safety, tolerability, PK, and preliminary efficacy study of INCB01824 1% cream applied QD and 1.5% cream applied BID. All adverse events (AEs) were mild to moderate in intensity and most judged unrelated to study medication, with no associated serious AEs (SAEs) or withdrawals. Laboratory and ECG evaluations did not suggest any safety issues, specifically no instances of neutropenia, thrombocytopenia, or leukopenia.

INCB 18424-202 was an open-label, multicenter, sequential-cohort, dose-escalation, safety, tolerability, PK, pharmacodynamics (PD), and preliminary efficacy study of Ruxolitinib cream 1.0% or 1.5% applied to 2% to 20% BSA QD or BID for 4 weeks. Application area increased sequentially, and alternative dosing paradigms were explored at the highest application area. The efficacy analyses collectively demonstrated efficacy of all 5 regimens of Ruxolitinib cream in psoriasis. The incidence of all reported AEs, the clinical laboratory results, vital signs, and ECG findings showed no confirmed safety signals or trends. Mean topical bioavailability ranged from 3.4% to 5.2% with no significant inhibition of cohort mean PD. Overall, Ruxolitinib cream (1.0% or 1.5%) was demonstrated to be safe and well tolerated when applied QD or BID for 28 days to plaque psoriasis affecting 2% to 20% of the BSA.

INCB 18424-203 was a double-blind, randomized, multicenter, parallel group, vehicle-controlled dose-ranging study with application of Ruxolitinib cream or vehicle in subjects with stable plaque psoriasis. Overall, Ruxolitinib cream (0.5%, 1.0%, or 1.5%) was demonstrated to be safe and well tolerated when applied QD for 12 weeks to plaque psoriasis affecting 2% to 20% of the BSA.”

Study INCB 18424-206 was a double-blind active- and vehicle-controlled study in adults with AD. Three hundred seven participants were randomized, and 306 participants received blinded study treatment. Those who received treatment in the 1.5% ruxolitinib cream BID arm achieved a significantly larger improvement from baseline when compared to the vehicle treatment group. Thus, we propose to use that same dosing regimen in this trial as it has demonstrated efficacy in treatment of AD and psoriasis in other trials.

## 1.6 Risks and Benefits

### Benefits:

Others with NL may benefit in the future from what we learn in this research study. It is possible their symptoms could also improve while being treated with this study drug

Risks:

The following adverse events were reported as very common Side effects associated with the use of Ruxolitinib cream:

- Very common (occurring in greater than or equal to 10% of subjects), common (occurring in 1-10% of subjects), and rare (occurring in 0.1% of subjects) side effects occurring in subjects. As of the clinical data cutoff date, 793 unique participants have been exposed to ruxolitinib cream and 515 participants have been randomized in ongoing blinded studies in AD, where participants receive 0.75% ruxolitinib or 1.5% ruxolitinib or vehicle in a 2:2:1 ratio. The most frequently reported TEAEs in healthy participants and participants with psoriasis, AA, AD, and vitiligo are listed below.

Indication	N	TEAEs by PT ( $\geq 6$ participants)
Healthy participants	41	No TEAEs at the time of data cutoff
Psoriasis	203	Upper respiratory tract infection, nasopharyngitis, application site irritation, headache, application site pruritus, abnormal ECG QT interval, pruritus, sinusitis
AA	83	Nasopharyngitis, pruritus, sinusitis
AD	314	Nasopharyngitis, upper respiratory tract infection, headache, atopic dermatitis
Vitiligo	152	Acne, viral upper respiratory tract infection, application site pruritus, pruritus, upper respiratory tract infection, sinusitis, bronchitis, influenza, oral herpes, application site erythema, diarrhea, headache, skin exfoliation

**Very Common (affecting more than 10 in every 100 patients )**

Pruritus (itching)
Upper respiratory tract infection / nasopharyngitis (common cold)
Dry Skin
Headache
Acne
Application site redness / irritation

Common (affecting less than 10 in every 100 patients)	
Change in ECG tracing	Abdominal pain (stomach pain)
Sinusitis (sinus infection)	Muscle strain
Back Pain	Throat Pain
Diarrhea	Psoriasis (skin disorder under treatment)
Liver enzyme increased	Blood sugar increased
Gastroenteritis (vomiting/diarrhea caused by virus)	Cholelithiasis (stone in gall bladder)
Influenza (flu)	Cough / Bronchitis
Pneumonia (lung infection)	Cystitis (irritation of bladder)
Fever	Bulging disk in back
Skin peeling	Blood cell count decreased
Ear infection	Mouth pain
Atopic Dermatitis (treatable skin condition)	Urinary tract infection
Bursitis	Tendonitis
	Oral herpes

Rare but Serious
Asthma
Psychosis exacerbation (worsening delusions, paranoia)

**Photosensitivity:**

There may be a risk of skin reaction to the combined exposure of ruxolitinib and sunlight.

**Hematologic abnormalities:**

Ruxolitinib taken systemically can inhibit the growth of blood cells. Low blood cells can make subjects more susceptible to infections by bacteria, virus, and fungi. The risk is low with systemic therapy and was not noted with topical therapy but subjects will be monitored for any signs of inhibition of their blood counts.

**Infection risk:**

There is a theoretical increase in risk of infection with topical use of ruxolitinib cream. This will be monitored for.

Ruxolitinib may increase risk of infections and reactivation of latent infections such as Tuberculosis or Valley Fever. Serious bacterial, fungal and viral infections were observed in patients receiving ruxolitinib. Please seek medical advice if signs or symptoms suggestive of infection occur.

**Allergy:**

It is possible that some people could have an allergic reaction to ruxolitinib cream.

**Cancer Risk:**

Ruxolitinib cream may have the potential to affect subject's immune system; they may be at increased risk for infections and possibly cancer. Live vaccines should not be given concurrently with ruxolitinib cream.

**Pregnancy Risk:**

The effect of the study drug on a fetus (developing baby still in the womb), or on a breastfeeding infant, is unknown and may be harmful. Because of these risks, women cannot take part in this study if they are pregnant or breastfeeding.

**Skin biopsy:**

A skin biopsy is generally a safe procedure, but some potential risks may include local pain, mild local bruising, bleeding, scarring, and an infection at the site where the skin biopsy was performed. If a topical antibiotic is used afterwards, then there is a small risk of an allergic reaction.

**Chest X-ray:**

Subjects will be exposed to radiation from the chest x-ray. The amount of radiation has a low risk of harmful effects.

**Blood draw:**

The risks of drawing blood include pain, bruising, lightheadedness, and/or fainting, or rarely, infection at the site of the needle stick.

**Other:**

As with all research, there is a chance that confidentiality could be compromised; however, we take precautions to minimize this risk.

## **2 Study Objectives**

**Primary Objective:**

To determine the efficacy of ruxolitinib cream as measured by the change in NL score (0-12) of the index treatment lesions (weeks 0 and 12). In prior psoriasis studies including Study INCB 18424-201 and Study INCB 18424-202, preliminary efficacy (change from baseline) was evident by Day 28. However, the single case report of NL treated with systemic ruxolitinib required 3 months of therapy. Therefore, we will request 12 weeks of therapy.

**Secondary Objective:**

To determine the efficacy of INCB018424 and the duration of response after discontinuation as measured by the change in 24 hour recall of Pruritus NRS, (week 0 to week 4, week 0 to week 8, week 0 to week 12, week 0 to 16, weeks 4 to 8, weeks 8 to 12, weeks 12 to 16), Change in Skindex-16 (week 0 to week 4, week 0 to week 8, week 0 to week 12, week 0 to 16, weeks 4 to 8, weeks 8 to 12, weeks 12 to 16), Change in Physician Global Assessment (PGA) (week 0 to week 4, week 0 to week 8, week 0 to week 12, week 0 to week 16, weeks 4 to 8, weeks 8 to 12, weeks 12 to 16), Change in BSA (week 0 to week 4, week 0 to week 8, week 0 to week 12, week 0 to 16, weeks 4 to 8, weeks 8 to 12, weeks 12 to 16), Change in NL Lesion Score (week 0 to week 4, week 0 to week 8, week 0 to week 12, week 0 to 16, weeks 4 to 8, weeks 8 to 12, weeks 12 to 16).

**Exploratory Objectives:**

To predict responses and examine the pharmacodynamics of treatment through the identification of unique biomarkers and transcriptomic changes of NL at week 0 and utilizing RNA sequencing on responsive and non-responsive tissue at week 4 To correlate these biomarkers with measures of global response: NL Lesion Score, PGA, and BSA.

### **3 Study Design**

#### **3.1 General Description**

This is a single center, exploratory, open-label, single-arm design study of 12 patients. Treatment naïve and treatment refractory patients with NL will be treated with ruxolitinib cream. Patients who are non-responders, to physician choice standard of care, such as topical, intralesional, and systemic or various non-steroidal including methotrexate, tumor necrosis factor alpha inhibitors, mycophenolate mofetil and fumaric acid esters will undergo a washout period and will be enrolled in the study.

Multiple safety studies have been conducted with ruxolitinib cream (see Safety) and a treatment regimen of 1.5% ruxolitinib cream BID on up to 20% BSA is deemed safe (Investigator's Brochure). Due to the thinned skin and potential for ulceration of NL, we will only treat up to 10% BSA Therefore, we propose a single center, exploratory, open-label, single-arm design study of 12 patients. Treatment naïve and treatment refractory patients with NL will be treated with ruxolitinib cream.

Individuals with NL will be eligible. All lesions will be treated, annotated, photographed, and scored. Prior treatment will be allowed; however, a washout period of 2 weeks for topical and 4 weeks for systemic agents which may alter disease course is required. At the washout period, individuals will undergo evaluation with a PGA, BSA calculation and NL lesion score lesion. Additional Pruritus measures using the NRS and Skindex-16 will be collected at that time.

Individuals will then initiate treatment on all lesions of NL BID and will be evaluated weekly and assessed by PGA, BSA, NL lesion score, Pruritus NRS, and Skindex-16 between weeks 0-4 (see Appendix). At week 12 will be the primary endpoint; however therapy will be continued for an additional 4 weeks. Therapy will be stopped and the individuals will be evaluated at week 12 and assessed by PGA, BSA, NL lesion score, Pruritus NRS, and Skindex-16. Laboratory and safety monitoring will occur at weeks 1, 2, 3, 4, 8, 12, 16. 3D photographs will be taken at weeks 0, 1, 2, 3, 4, 8, 12, 16. Individual lesions will be circled at that time and the exact volume of each lesion will be measured through use of 3D images. Up close photos will be taken of the disease and normal tissues attained at weeks 0 & 12.

Tissue will be collected for RNA sequencing at week 0 and 4. Blood collection will include the isolation at week 0, 2, 4, 8, 12. 5mL vials of blood which will be separated and the serum and cell

pellet will be stored for future analysis. Three skin biopsies will be taken during the study. At week 0, one 3mm tissue biopsy will be taken from lesional skin and one biopsy will be taken from non-lesional (adjacent but normal-appearing a minimum of 2 cm from the primary lesion but within the same anatomical subunit) skin. At week 4, a 3mm biopsy will be taken from a treated lesion (Ideally the same lesion as the initial biopsy, separated by a minimum of 1cm, or a similar lesion in the same anatomical subunit). The lesions will be chosen using full body photographs taken at week 0. From the biopsy specimen, a small piece of tissue (approximately 1 mm) will be cut and placed in a bottle labeled for RNAseq. The larger specimen will be placed in a bottle labeled for biobank storage. Both samples will be snap frozen and stored in the biobank. Once sample collection is completed for all samples, the tissues labeled for biobank storage will continue to be stored in the biobank and RNA sequencing will be performed on the tissue samples labeled for RNAseq (up to 36 tissue samples) and analysis will be performed. Paired analysis of treatment responsive and refractory lesions will be made as well as treated and untreated lesions.

**Nucleic Acid Extractions:** RNA will be extracted from a total of 50 um of fresh tissue using the Qiagen FFPE RNeasy Micro extraction Kit according to manufacturer's recommendation.

**RNA Transcriptome Sequencing:** RNA transcriptome sequencing will be carried out using commercially available techniques. Briefly, RNA libraries will be created using up to 100ng of RNA as starting material using the Illumina RNA TruSeq Library kit according to manufacturer's recommendation. Libraries will be QCed for quality and quantity using the Illumina TapeStation High Sensitivity tape. Paired-end sequencing will then be carried out on the Illumina HiSeq 4000 using 101bp insert fragments.

**Primary and Secondary Measures:**

All efficacy assessments will be performed prior to the administration of study treatment at each visit. The recommended order and the overall outline of measurements for the efficacy assessments are described below.

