**Efficacy measures:**

PGA, BSA, NL Lesion Score, Pruritus NRS, Skindex-16

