**Table-2: Screening and Visits (+/- 3 day window)**

	Screening	Day 0	Week 1	Week 2	Week 3	Week 4	Week 8	Week 12	Week 16
Ruxolitinib*		X	X	X	X	X	X		
Physical Exam	X	X	X	X	X	X	X	X	X
Adverse Event Assessment		X	X	X	X	X	X	X	X
Chest X-ray	X								
Assessments: PGA, BSA, lesional number, NL Lesion, Skindex-16, Pruritus NRS		X	X	X	X	X	X	X	X
Photographer		X	X	X	X	X	X	X	X
Skin Biopsy (tissue/serum bank)		X				X			
Urine Pregnancy Test	X								
Venipuncture	X	X	X	X	X	X	X	X	X
Biomarker/RNAseq blood (tissue/serum bank)		X		X		X	X	X	
CMP	X		X	X	X	X	X	X	X
CBC	X		X	X	X	X	X	X	X
Quantiferon Gold	X								
Hepatitis B	X								
Hepatitis C	X								
HIV	X								
Coccidioidomycosis	X								

\*Patients will receive 1.5% ruxolitinib cream tubes to apply cream at home BID inbetween visits to be applied from Day 0 through Week 12. Patients will not receive 1.5% ruxolitinib cream at Week 12 visit as this begins their follow up period.

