### **3.4 Primary Study Endpoints**

Change in NL score (0-12) of the index treatment lesions (weeks 0 and 12).

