### **Supplemental 1: Appropriateness of Measures**

**Skin Scoring:**

There are no validated skin scoring systems for NL. One prior publication developed a non-validated NL skin scoring system (0-12) which examines erythema, infiltration, ulceration, and pain. We will use other simple measures of BSA which is objective and PGA which is well validated in other inflammatory skin conditions. Additionally, we will simply annotate the number of lesions on the individual as a marker of total disease burden.

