## 14 Attachments

### Appendix:

Physician Global Assessment: 

Grade 0 Completely clear: no evidence of disease (100% improvement) CCR

Grade 1 Almost clear: very significant clearance ( $\geq 90\%$  to  $<100\%$ ) PR

Grade 2 Marked Improvement: significant improvement ( $\geq 75\%$  to  $<90\%$ )PR

Grade 3 Moderate improvement: intermediate between slight and marked ( $\geq 50\%$  to  $<75\%$ ) PR

Grade 4 Slight improvement: some improvement ( $\geq 25\%$  to  $<50\%$ ); however, significant evidence of disease remains SD

Grade 5 No change; disease has not changed from baseline condition (+/- $<25\%$ ) SD

Grade 6 Worse, disease is worse than at baseline evaluation by ( $\geq 25\%$ ) or more PD

CCR- Complete clinical response

PR- Partial response

SD- Stable disease

PD- Progressive Disease

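### The suggested assessment order puts the improvement-graded PGA before the primary NL score and the patient questionnaires last, an avoidable bias risk in an open-label, single-arm trial

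*Combined protocol and SAP*

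**What the plan says.** Under Primary and Secondary Measures, Section 3.1 requires efficacy assessments to precede dosing at each visit and adds that "The recommended order and the overall outline of measurements for the efficacy assessments are described below". The next item, headed Efficacy measures, is an unnumbered line: "PGA, BSA, NL Lesion Score, Pruritus NRS, Skindex-16".

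Two other places have the PGA first and the questionnaires last. The design narrative in Section 3.1 has subjects "assessed by PGA, BSA, NL lesion score, Pruritus NRS, and Skindex-16 between weeks 0-4", and repeats that sequence for the week 12 evaluation. The Table-2 row reads "Assessments: PGA, BSA, lesional number, NL Lesion, Skindex-16, Pruritus NRS"; it adds lesion number and swaps the two questionnaires.

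The PGA in the Section 14 Appendix is a rating of change, not of current severity. One grade reads "Grade 5 No change; disease has not changed from baseline condition", and another "Grade 3 Moderate improvement: intermediate between slight and marked". Each of the seven grades is tied to a percentage change or to its absence.

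The primary endpoint (Section 3.4) is the change in the 0-12 NL score of the index lesions between weeks 0 and 12. Supplemental 1 says of this score: "One prior publication developed a non-validated NL skin scoring system (0-12) which examines erythema, infiltration, ulceration, and pain". Each of the four items is graded 0 to 3 with one-word anchors.

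**The concern.** An assessor who follows the list records a verdict on progress and then scores four coarse items that should be judged on the lesion as it looks and feels that day. The second rating can be drawn towards the first. This need not cancel in the change from baseline: Table-2 schedules the PGA at Day 0 too, but there is then no improvement to grade, whereas at week 12 there is. With one open-label arm, any shift in the week 12 score passes directly into the estimate.

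The subject answers the Pruritus NRS and Skindex-16 after the lesions have been examined and graded, so anything conveyed during the examination could affect the answers. Pain, which the subject has to report, is also scored after the PGA.

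Two uses of the data raise the stakes. Supplemental 1 brings in the PGA and BSA as further measures because no validated NL score exists; agreement between PGA and NL score is weaker support if one was graded just before the other. Sections 7.1 and 7.2 say that the estimated effect sizes will inform the size of later studies, so a distorted estimate would carry over into them.

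**Working it through.** The plan gives no figure on this point to reproduce. It states no effect size, standard deviation or power, and Section 7.2 sets 12 subjects on logistical and financial grounds. The check is a comparison of passages plus scale arithmetic.

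**1. Is any other order set?**

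| Place | Position of PGA | Position of NL score | Position of questionnaires |
|---|---|---|---|
| Section 3.1, Efficacy measures | 1st of 5 | 3rd | 4th and 5th |
| Section 3.1, narrative (twice) | 1st of 5 | 3rd | 4th and 5th |
| Table-2, assessments row | 1st of 6 | 4th | 5th and 6th |

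The secondary outcome list in Section 3.1, the secondary objective in Section 2 and Section 3.5 name the Pruritus NRS first. They list endpoints with their time intervals and do not describe how a visit runs. The follow-up visit lists in Sections 6.3 to 6.9 begin with physical examination, questions on side effects and skin examination. They never mention the questionnaires, so nothing there places them earlier.

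**2. Is there a separate safeguard?** The documents provide for no independent or masked rater of the NL score, no scoring from coded photographs, and no completion of questionnaires before the examination.

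**3. Which endpoints are exposed?** Section 3.5 lists six measures (Pruritus NRS, Skindex-16, PGA, BSA, NL score, lesion volume) over seven intervals: 6 x 7 = 42 contrasts. The NL score and the two patient-reported measures make 3 x 7 = 21 of the 42. The primary endpoint is exposed as well; the secondary NL contrast from week 0 to week 12 repeats it.

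**4. Leverage on the primary score.** Four items x 3 points = 12. A one-grade shift on one item moves the score by 1/12 = 8.3% of its range. The pain item is 3/12 = 25% of the range.

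**5. Illustration of size (both inputs assumed, neither from the documents).** Take a true fall of 3 points and a shift of 0.25 to 1 point towards improvement. Share of the reported change = shift / (true fall + shift):

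- 0.25 / 3.25 = 7.7%
- 1 / 4 = 25%

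A shift of the same size the other way would give reported falls of 2.75 to 2 points.

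**The case against.** **The order may not be an order.** It is only recommended, the list is unnumbered, a schedule row such as Table-2 does not by itself set a sequence, and the two disagree on the order of the questionnaires. This stands as a reason for moderate confidence. It does not remove the point. Section 3.1 promises an order, the line directly beneath is the natural candidate, and the narrative and Table-2 agree on PGA first and questionnaires last. If the line was not meant as the order, the promised order is missing and the same edit is needed.

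**Conduct is inferred.** A reader might conclude that subjects are told their PGA grade, or that one person always gives both ratings. The documents say neither. The preference for the same staff member in Section 3.6 applies if possible and sits under safety endpoints. Influence on patient reports is therefore a risk and not a described event.

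**Direction.** A reader might infer that the bias always favours the drug. That is not supported: the PGA has grades for no change and for worsening, so anchoring could pull either way. The contrasts from week 12 to week 16 fall, by Table-2, after treatment.

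**Partial safeguards exist.** Lesion volume is measured from 3D photographs, which gives a less rater-dependent comparison, and Section 2 ties the itch rating to a 24-hour recall. Both help, but neither protects the NL score.

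**Purpose.** This is a small pilot meant for estimation. That limits the consequence, but bias matters when estimation is the aim.

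**Conclusion.** The point holds as an avoidable risk that is cheap to remove. It does not show that the results will be biased. As written, the plan suggests recording a rating of change before the primary score and before the patient reports, in a trial with neither masking nor a control arm to absorb the effect. The primary endpoint and 21 of 42 secondary contrasts are exposed, and a quarter of the primary scale is a symptom that the subject must report.

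The conclusion rests on reading the Efficacy measures line as the announced order. The size and direction of any bias cannot be derived from the documents. The range of about 8% to 25% of the reported change depends wholly on the assumed 3-point fall and the assumed shift of 0.25 to 1 point towards improvement. A reader might put the upper end at one third, but 1/3 is the shift relative to the true fall; relative to the reported change it is 1/4.

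**What to change.** In Section 3.1 and Table-2, replace the unnumbered lists with one numbered order for every visit:

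1. The subject completes the Pruritus NRS and Skindex-16 before the examination or any comment on progress.
2. Lesion pain is asked; erythema, infiltration and ulceration are scored; the NL score is then locked on the CRF.
3. Lesion count and BSA are recorded.
4. The PGA is graded last.

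Apply this to subjects who have not yet had Day 0, so that each subject's baseline and week 12 scores are taken in the same order. Switching everyone at their next visit would mix orders within the change from baseline for subjects already under way, and recording the date of the switch would not undo that. Report which order each subject had.

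The cost is protocol wording and a CRF page order, with no added visits, staff or procedures. There are two limits. Subjects already enrolled keep the old order, so a 12-subject data set may hold both. Reordering also removes only the order effect: rater and subject still know the treatment and the visit.
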